Research Protocol: 18F-DOPA PET to Elucidate the Antidepressant Mechanism of Lurasidone in Bipolar Disorder

9/17/2019

Recruitment Procedures

Patients will be recruited through referrals from treating outpatient psychiatrists, or from clinics at Columbia University. Advertisements will be placed through the Columbia University website including the "RecruitMe" site and on advertising sites such as Craig's List. A website that describes the study will be created. Messages will be posted on email list-serves of mental health clinicians describing the study and asking for referrals. Subjects will be recruited by Depression Evaluation Service members through IRB#6669R.

Study staff and investigators will contact subjects who respond to advertising efforts to screen and recruit eligible individuals. For clinical patients at Columbia, only subjects who the clinical staff has identified as appropriate will be approached. The clinical staff will first ask the patient if he or she can be approached by research staff. Only if the subject agrees to be approached will the staff from this study do so. All potential subjects will be given the telephone number of the research coordinators who will discuss the purpose and procedures of the research and screen the subjects for potential eligibility.

Texts of written materials to be distributed via advertisements and websites will be submitted to the IRB for approval before they are distributed.

1. Initial screening will be completed as detailed in IRB#6879R or IRB#6669R.

2. If eligible, subjects will be asked to sign the consent form for IRB# 4815 ([name]). Participants will then be given a physical exam, laboratory test (via blood draw) and psychiatric examinations as performed under IRB#4815. IRB#4815 allows for clinical assessments, a medical screening for significant illness, a screening for drugs of abuse, a developmental history and acquisition of blood samples for genetic analyses. IRB#4815 allows for the above procedures so that subjects can enter any of several different types of studies and protocols.

3. If eligible for IRB#4815, subjects will be given a detailed verbal explanation of this study by a research psychiatrist. During the consent process, the consenting psychiatrist will obtain a history of participants' past radiation exposure. Participants will then give written informed consent if they choose to participate in the study.

Inclusion Criteria

Criterion	Method of Assessment
1)Ability to provide informed consent	Clinical interview
2) Diagnosis of bipolar I disorder, bipolar 2 disorder or	DSM-IV by means of SCID
bipolar disorder NOS and currently meeting criteria for a	
major depressive episode	
3) Depression of sufficient severity to score at least 16 on the	Hamilton Depression Rating
first 17 items of the Hamilton Depression Rating Scale	Scale
including the atypical depression items addendum	
4) Age 18-50 years old	Clinical interview

5) Patients who were on psychiatric medication at	Clinical interview
presentation will have failed that regimen, as defined as not	
achieving at least partial remission after an adequate dose of	
medication for at least six weeks. Benzodiazepines and	
hypnotics are allowed throughout the study	
6) Females of child-bearing potential must be willing to use	Clinical interview
an acceptable method of birth control throughout the study:	
abstinence, birth control pill, male condom, IUD, depo-	
provera, Norplant, male sterilization or female sterlization	
7) Subject is likely to tolerate medication washout if	Clinical interview
indicated	
8) Must be enrolled in IRB#4815	Review of records

Exclusion criteria

Criterion	Method of Assessment
1)Diagnosis of any other major psychiatric disorders such as	As defined by DSM-IV by
schizoaffective disorder, current psychotic depression, or	means of SCID; urine drug
current drug or alcohol abuse (within two months before the	screen
study) or recent drug or alcohol dependence (within six	
months before the study); anorexia nervosa or bulimia	
nervosa within in the last year; Meet DSM-IV criteria for	
manic episode at the time of screening	
2)Previous failed trial of lurasidone, defined by at leastv six	Clinical interview
weeks of treatment at the dose of 20 mg per day or more.	
Experienced intolerable side effects of lurasidone in the past.	
Taking any medications that are contraindicated with	
lurasidone unless there is a plan to stop these as part of the	
washout.	
3)History of clinical deterioration when any of the	Clinical interview
medications that the patient is taking at presentation have	
been discontinued in the past if they will be discontinued as	
part of the washout.	
4)First-degree family history of schizophrenia if the subject	Clinical interview
is less than 33 years old.	
5)Significant active physical illness, including blood	Medical history by a
dyscrasias, lymphomas, hypersplenism, endocrinopathies,	physician, physical exam,
renal failure, chronic obstructive lung disease, autonomic	screening lab tests (chemistry
neuropathies, peripheral vasucalar disease, malignancy,	panel [SMAC20], CBC, HCG
neuromuscular disorder or tardive dyskinesia. Any medical	test for pregnancy, urinalyzsis
diagnoses that would be a contraindication to lurasidone	and TSH under IRB#4815
treatment. Hemoglobin <11 in females or <13 in males	
6)Actively suicidal, as defined by expressive ideation with a	Clinical interview and score of
plan for suicide or develops suicidal ideation that requires	5 or greater on CSSRS
immediate medical or treatment intervention	

7)Pregnancy, abortion or miscarriage in the two months prior	Clinical interview and serum
to enrollment or plans to conceive during the course of the	pregnancy test at screening
Study participation	Clinical interview
0)ECT within the next six months	Clinical interview and chart
9)EC1 within the past six months	review
10)Subjects who endorse a history of prior head trauma and	Clinical interview and
score 1.5 standard deviations below the mean of Trailmaking A & B	trailmaking A & B as needed
11)Metal implants, pacemaker, metal prostheses, metal	Clinical interview; written
orthodontic appliances or shrapnel in the body unless there is	confirmation from health care
confirmation that the substance is MRI compatible	provider if warranted
12)Current, past or anticipated exposure to radiation	Clinical interview
including	
	Study team will check our
a) Having been badged for radiation exposure in the	database to ensure that the
	subject has not participated in
b) Clinical judgement that past lifetime radiation	an imaging study within our
DET scene in the summent study inedvise he	Division in the past year.
a) Participation in public modicing protocols in the	
last year*	
lust your	
* Subjects will be eligible, however if the injected dose and	
dosimetry of the radiotracer are known and the cumulative	
annual exposure of the previous study and this sutdy is lower	
than the annual limit fo research subjects defined by the	
FDA (21 CFR 361.1)	
13)History of claustrophobia that would prevent	Clinical interview
participation in imaging scans	
14)Obesity with weight >350 lbs or inability to fit into the	Medical evaluation and testing
MRI scanner	at MRI suite if needed
15)Inadequate understanding of English	Clinical interview
16)Concurrent anticoagulant or anti-platelet treatment	Clinical interview
including aspirin if it is needed daily	

Research Procedures

`Medication Washout: If patients are eligible to participate in the study, and they are taking psychiatric medications at the time of recruitment, they will have the psychiatric medications tapered off. The patients will be off of all medications for three weeks before PET scanning. This medication-free treatment period is necessary to obtain imaging and clinical outcome data that are not significantly influenced by previous medications. The design will also allow us to measure the clinical response to lurasidone that is independent from an interaction with the previous medications. Patients will meet with a psychiatrist from MIND or DES at least weekly

in person during this time. A CGI, HAM-D, YMRS, psychotic symptoms of BPRS and CSSRS will be performed at least weekly to detect new onset of manic symptoms or clinical deterioration. Only patients who still meet inclusion criterion of HAM-D>15, including atypical depression items addendum, at the clinical appointment one week before the scheduled PET scan will continue.

Patients who no longer meet inclusion criteria at the end of the period, including those that are no longer sufficiently depressed, will not continue with imaging and will be offered up to 6 months of open label outpatient treatment.

Frequency of Clinical Visits: Throughout the study, outpatients will meet with a treating MIND or DES psychiatrist at least once a week in-person. Subjects will do the washout on the 4 Center or 5 South unit if clinically warranted. Inpatients will be evaluated by their physician at least three times weekly. In addition, all inpatients are monitored at intervals on an around-the-clock basis by ward clinical staff. During the washout period, inpatients will generally see a psychiatrist daily, except for weekends and holidays.

MRI Scans: All subjects will have an MRI of the brain to obtain information on brain structure to co-register PET data. MRI scans will be obtained at the NYSPI MRI facility using a 3.0 Tesla GE scanner. Females of child bearing potential will have a urine hcg test within 24 hours of the scan. Subjects will have the option of visiting the MRI suite before the scan to enter a mock (fake) MRI scanner. The mock MRI scanner has the same dimensions as the real scanner so it allows participants to experience what it is like to be inside the actual magnet. The purpose of this is to have the subject be as comfortable as possible before the actual scan. Patients will receive an MRI scan lasting not more than 30 minutes. Structural scans will include T1-weighted and diffusion tensor imaging sequences. The procedure will be immediately stopped if the participant reports significant distress.

PET Imaging: Each subject will undergo two PET scans with [18F]DOPA at the David A. Gardner PET Center at [name]. One scan will be before lurasidone is initiated and the second will be four weeks (+/- one week) after starting lurasidone. Patients will not eat within 12 hours of the PET scan with the exception of a low-protein meal more than four hours before the scan. A urine pregnancy test will be done on females on the day of each PET scan, before the scan, to assure that pregnancy has not occurred between the time of laboratory tests at screening, during which a serum pregnancy test is conducted, and the PET scan. Patients will be given 150 mg of carbidopa PO within 120 minutes of the radiotracer injection. Carbidopa is used to prevent AAAD decarboxylation of the radiotracer so that it is bioavailable to cross into the brain. The subject will have an intravenous line placed for radiotracer injection. An arterial line will be placed in the radial artery of the other arm by an experienced physician, [name]. [name] will be present during the scan until the arterial line is removed. An MD clinician from the MIND Division will be on the CUMC campus and avilable during the scan via telephone. If [name] is not available, [name] or [name] will be present during the scan until the arterial line removed. Patients will have vital signs measured before radiotracer injection and after PET scan is complete. If there is an complication with the arterial line placement, including patient refusal at the time of scan, the scan will proceed without blood sampling.

The subject will be placed in a supine position on the camera bench. A head holder will be used to decrease head movement during the scan. A low dose computer tomography scan will be used to obtain data for attenuation correction. 5 mCi or less of [18F]DOPA will be administered I.V. over about 60 seconds. The emission scan will be initiated at the time of injection and emission data will be obtained for 90 minutes or less. During the emission scan, arterial samples will be drawn at 10 second intervals for the first two minutes and every 30 seconds for the second two minutes using an automated blood sampler. Thereafter, manual samples will be drawn at 6, 8, 10, 15, 20, 50, 75 and 90 minutes. Radioactivity in the plasma will be measured using a gamma counter. If the patients need to get up from the scanner for any reason, the low dose attenuation computer tomography scan will be repeated once only per PET scan. Patients will have a clinical check in with a study physician within 48 hours of the PET scan for safety evaluation that will include an administration of CSSRS. Patients will have a urine pregnancy test conducted after the PET scan within 2 weeks of the scan.

Clinical Treatment: Open-label lurasidone will be taken by participants after a meal, beginning at 20 mg daily for the first two weeks. At that time, the dose can be increased to 40 mg daily for two weeks. Dosage will be raised only if the participant is tolerating the medication and has not been rated "much improved" or "very much improved" on the CGI improvement scale for that week. At week 4, blood samples will be drawn to measure blood glucose and lipids for safety monitoring. Treatment will be up to 4 weeks or until the second PET scan. Study visits will be weekly with a MIND or DES psychiatrist, unless the participant is rated much improved at week four, in which case visits will be biweekly thereafter. Additional visits can be scheduled at the study doctor's discretion for purposes of clinical management. At each visit, the study psychiatrist will complete the MADRS, YMRS, CGI, CSSRS, psychotic symptoms of BPRS, and SAFETEE-GI. Patients will complete self-rating forms at each visit. Participants with a Clinical Global Improvement (CGI) score of 6 ("much worse") or 7 ("very much worse") on two consecutive weeks during the trial will be terminated early from the study. Patients without alcohol or benzodiazepine use disorder may receive benzodiazepines for insomnia or anxiety/agitation (maximum dose equivalent to 4 mg of lorazepam per day). All patients may also receive zolpidem or diphenhydramine for insomnia or agitation.

Lurasidone and all laboratory tests will be provided for free of charge to the participant. Participants will receive six months of free outpatient treatment including the treatment obtained through this protocol, with treatment visits at least monthly.

Emergency Procedures: A research psychiatrist will be available by cell phone at all times during the study. Patients requiring urgent admission at the time of a study visit will be brought to the CUMC Emergency Department by the study physician and if necessary, security assistance will be provided. The treating psychiatrist will arrange non-urgent hospital admissions, preferably to the NYSPI 5-South unit. If patients refuse hospitalization but the clinical team determines that this is needed, the team will arrange all necessary interventions including contacting the local crisis team, family or Emergency Medical Services.

Patients lost to follow-up: Upon enrollment, patients will be asked to provide the name and phone number of at least two persons who will likely know their future whereabouts. These people will be contacted if the subject is lost to follow up.

Criteria for Early Discontinuation

1) Intolerable side effects of lurasidone

2) Refusal to continue regimen and willingness to receive open treatment 3) DSM-IV criteria for a manic episode or score > 12 on the YMRS

4) During the washout period, if subjects score a six (much worse) or seven (very much worse) on the CGI- I, the protocol will be discontinued. If the participants do not tolerate the washout because of marked agitation, severe anorexia such as inability to drink adequate amount of fluids, or suicidal ideation or behavior with plan or intent, the protocol will be discontinued. In these cases, subjects will be offered open clinical treatment.

5) During the lurasidone treatment phase, if subjects score a six (much worse) or seven (very much worse) on the CGI-I for two consecutive weeks, the trial will be terminated early. If there is clinical reason to change to open treatment, such as onset of psychotic symptoms, manic symptoms of clinical concern, active suicidal ideation on two consecutive visits, the clinical team will evaluate whether the risks outweigh the benefits of continuing protocol.

6) If the patient requests withdrawal for any reason.

7) The PI judges that it is medically unwise to continue in the study, for example if the subjects are unable to comply with the study procedures and rules.

Radiotracer Information

Name of the radiolabeled drug/compound: [18F]DOPA

Manufacturer and other information: [18F]DOPA will be synthesized by the David Gardner PET Center at CUMC. IND 140398 is to use [18F]DOPA with lurasidone (latuda) as per this PSF. Lurasidone (Latuda) will not be used in an off label manner, however.

IND is approved IND# 140398. IND is held by PI/CU Investigator [name], MD

Data Analysis Plan

The aim of the analyses is to provide feasibility data for a larger grant application. We will visualize all data to assess for trends that are not detectable in standard statistical analyses due to the small power of this preliminary study.

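### Sedatives are allowed throughout a trial whose baseline scan is described as medication-free, and nothing keeps their use the same at the two paired [18F]DOPA scans

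*Combined protocol and SAP*

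**What the plan says.** Under Research Procedures, Medication Washout, psychiatric drugs are tapered and "The patients will be off of all medications for three weeks before PET scanning". The reason follows: "This medication-free treatment period is necessary to obtain imaging and clinical outcome data that are not significantly influenced by previous medications". No exception is stated there.

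Inclusion criterion 5 states that benzodiazepines and "hypnotics are allowed throughout the study". It sets no dose limit and no timing relative to a scan.

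PET Imaging schedules one scan before lurasidone and a second four weeks after it starts, give or take one week. It fixes the patient's food intake and a 150 mg carbidopa dose before the scan. It does not mention sedatives.

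Clinical Treatment, which describes the lurasidone phase, permits benzodiazepines up to 4 mg/day lorazepam equivalent for insomnia, anxiety or agitation in patients without an alcohol or benzodiazepine use disorder. It permits zolpidem or diphenhydramine for everyone. None of this is tied to scan timing.

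The Data Analysis Plan describes a small preliminary study meant to yield feasibility data, with all data inspected visually for trends.

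**The concern.** Each patient serves as his or her own control. There is no comparison arm, treatment is open-label, and the change from scan 1 to scan 2 is to be read largely by eye. Time and expectancy cannot be removed from such a comparison. Concomitant sedative use is different, because it can be held steady or at least noted.

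The plan treats freedom from earlier drugs as necessary for interpretable imaging, and a benzodiazepine continued from before enrolment is an earlier drug. The permitted reasons for sedatives are insomnia, anxiety and agitation, which may well change during treatment, so use need not be constant within a patient. If a patient takes a sedative before one scan and not the other, that patient's line in a paired plot shows both changes at once, and a reader of the plot would not know it.

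**Working it through.** The plan gives no figure to reproduce, and no arithmetic applies. The documents state no sample size, no rate of sedative use, and no effect of sedatives on [18F]DOPA uptake or on the ratings. The check is a comparison of the relevant sections.

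1. **Which scan the washout sentence covers.** The second scan is done on lurasidone, so a three-week drug-free interval can apply only to the first.

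2. **Whether it means every drug.** It does not. Criterion 6 accepts hormonal contraception in a list that begins "abstinence, birth control pill, male condom, IUD, depo". Criterion 7 makes washout conditional: "Subject is likely to tolerate medication washout if" indicated. Exclusion 3 concerns drugs whose earlier withdrawal led to deterioration, and applies to those that have "been discontinued in the past if they will be discontinued as" part of the washout. The washout is therefore selective, and criterion 5, the specific rule, most naturally governs sedatives.

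3. **Sedative status allowed at each scan.**
   - Scan 1, with criterion 5 as the exception: benzodiazepines and hypnotics allowed, with no cap stated.
   - Scan 1, read literally: none for three weeks.
   - Scan 2, at 3 to 5 weeks of lurasidone (4 − 1 to 4 + 1): benzodiazepines up to 4 mg/day lorazepam equivalent for those without the named use disorders, and zolpidem or diphenhydramine for all.

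   Under either reading of scan 1, a patient may be on a sedative at one scan and off it at the other.

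4. **Whether anything links the two scans.** PET Imaging and Clinical Treatment contain no hold, no stable-dose rule and no same-use rule for sedatives.

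5. **Whether a change would be visible.** The instruments named for washout and treatment visits are rating scales and a side-effect form. Self-rating forms are also mentioned, but their content is not given. No stated record ties drug, dose and last intake to a scan, and the Data Analysis Plan does not mention sedatives.

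6. **Whether the treatment-phase limits could simply be applied to the washout.** Exclusion 1 bars "current drug or alcohol abuse (within two months before the" "study) or recent drug or alcohol dependence (within six" months before it. A patient with an older disorder can therefore enter, and criterion 5 does not stop that patient, or one on more than 4 mg/day, from continuing a benzodiazepine. Imposing the cap or the use-disorder limit before scan 1 could force a taper. It could also exclude the patient under exclusion 3 if stopping that drug had caused deterioration before.

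**The case against.** The best case against the point is that the documents already resolve the conflict. Criterion 5 is specific, covers the whole study, and sits with other wording that shows a selective washout. Allowing sedatives in unmedicated, depressed bipolar patients is a sound safety choice. The study is a feasibility exercise with no stated test, power or decision rule for sedatives to upset. Most of this stands, and it is why the point is minor. It does not supply a common condition at the two scans, which is absent under either reading.

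A reader might infer more than the documents support, in four ways:

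- **That the protocol contradicts itself irreconcilably, leaving taper and eligibility undecided.** On the natural reading sedatives are exempt, exclusion 3 is not triggered by them, and one clause settles the matter.
- **That sedative use goes unrecorded.** The documents only fail to state a record. One may exist in clinic charts, in the self-rating forms or under the linked protocols (IRB#4815, 6879R, 6669R), and patients see a study psychiatrist weekly.
- **That the share of affected pairs can be estimated.** It is 0% if each patient's use is constant, and otherwise depends wholly on an assumed rate of use.
- **That the scans are biased.** Nothing in the documents shows that benzodiazepines, zolpidem or diphenhydramine alter [18F]DOPA uptake.

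**Conclusion.** The point holds as a minor, inexpensive improvement. The washout text promises a medication-free baseline that criterion 5 does not require, and the plan does not keep sedative use alike at the paired scans. A within-patient sedative change therefore cannot be told apart from a lurasidone change in the planned plots.

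Its size and direction cannot be computed. The conclusion rests on two things: that criterion 5 is the intended exception, and that some patients' sedative use may differ between scans. The first is well supported by the surrounding criteria. The second is permitted by the text, but its frequency is unknown. No stated test, power or conclusion of the trial is shown to be wrong.

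**What to change.** 1. **Medication Washout:** state that patients are off all psychiatric medications except the benzodiazepines and hypnotics allowed under criterion 5.

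2. **PET Imaging:** apply the same condition before both scans where clinically possible. Regular users stay on an unchanged dose. As-needed users, including those taking zolpidem or diphenhydramine, skip as-needed doses for one pre-set interval, the same before each scan. The study physicians should fix that interval in advance. If the condition cannot be kept, the scan goes ahead.

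3. **Record and plots:** at each scan, note drug, dose and time of last sedative. In the planned visualisations, mark pairs whose status changed, as description only. This includes patients who start or stop regular use between scans, and any whose dose had to change because of the treatment-phase limits.

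The 4 mg/day cap and the use-disorder limit in Clinical Treatment should not be carried back into the washout, because that could force tapers or affect eligibility through exclusion 3.

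The cost is a few words of protocol text, one record line per scan, and slightly less freedom to use as-needed sedatives just before scanning. The pre-scan condition asks no regular user to taper, and no scan is forgone because the condition was missed.

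### One fixed three-week washout for every stopped drug does not assure a clean first PET scan when a prior drug is slow or a depot

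*Combined protocol and SAP*

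**What the plan says.** Under Research Procedures, Medication Washout, eligible patients on psychiatric drugs "they will have the psychiatric medications tapered off". Then: "The patients will be off of all medications for three weeks before PET scanning". The length of the taper is not given. The protocol calls the drug-free period necessary for "imaging and clinical outcome data that are not significantly influenced by previous medications", and adds that it lets the response to lurasidone be measured free of interaction with earlier drugs.

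Other places bear on this:

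- **Inclusion item 5** requires that a patient on medication at "presentation will have failed that regimen, as defined as not" reaching at least partial remission. It also lists the one stated exception to stopping drugs: benzodiazepines and "hypnotics are allowed throughout the study".
- **Exclusion item 2** bars drugs contraindicated with "lurasidone unless there is a plan to stop these as part of the" washout. Such drugs may therefore be among those stopped.
- **Exclusion item 3** begins "History of clinical deterioration when any of the" and removes patients who worsened in the past when a drug now due for washout was stopped.
- **The check before scan 1** is clinical: "Only patients who still meet inclusion criterion of HAM-D>15" at the visit one week earlier go on.
- **PET Imaging** places scan 1 before lurasidone and scan 2 at 28 days, give or take 7, from its first dose. Lurasidone is open-label (Clinical Treatment), and no control arm is described.
- **Data Analysis Plan** aims at feasibility data for a larger application. It relies on looking for trends by eye, because power is small.

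**The concern.** A fixed number of days clears a drug only if the drug is fast enough. Nothing in the public text lengthens the three weeks for a slow drug or a depot, excludes such drugs, or asks for a drug level or half-life check before scan 1. A patient can follow the rule exactly and still carry drug at that scan.

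The paired PET change is what is chiefly at stake. In an affected patient the old drug goes on falling between the scans while lurasidone exposure begins. Without a control arm, the pair cannot separate the two.

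For mood the worry is weaker. The presenting regimen must have failed, patients known to worsen on stopping are excluded, and severity is rechecked before scan 1. None of these safeguards addresses the imaging signal.

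**Working it through.** The plan states three weeks without a derivation, so it has no figure of its own to reproduce.

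**Inputs from the documents.** Drug-free interval before scan 1: 21 days. Scan 2: 21 to 35 days after lurasidone starts.

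**Assumptions.** First-order elimination; half-lives h of 7, 16, 25 and 49 days (the documents give none); lurasidone starting right after scan 1, so that scan 2 falls 42 to 56 days after the last dose. For a depot, h stands for the release half-life, and a single exponential is itself an approximation.

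**1. Longest half-life that 21 days clears.** If a share r of the treatment level is tolerated and the taper has already brought the level to a share c, then h = 21 / log2(c/r).

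| Tolerated residual | No taper effect (c = 1) | Taper halved the level (c = 0.5) |
|---|---|---|
| 3.1% (five half-lives if c = 1) | 21/5 = 4.2 days | 21/4 = 5.25 days |
| 10% | 21/log2(10) = 21/3.32 = 6.3 days | 21/log2(5) = 21/2.32 = 9.0 days |

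The limit is therefore a range of about 4 to 9 days, not a single value.

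**2. Drug left at each scan, no taper effect.** Remaining = 2^(-t/h), as a percentage of the last-dose level.

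| h (days) | Scan 1, t = 21 | t = 42 | t = 56 | Fall from scan 1 to scan 2 (points) |
|---|---|---|---|---|
| 7 | 12.5 | 1.6 | 0.4 | 10.9 to 12.1 |
| 16 | 40.3 | 16.2 | 8.8 | 24.1 to 31.4 |
| 25 | 55.9 | 31.2 | 21.2 | 24.7 to 34.7 |
| 49 | 74.3 | 55.2 | 45.3 | 19.1 to 29.0 |

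The overall fall is 11 to 35 points. If lurasidone starts a week later (t = 49 to 63), it is 12 to 38 points.

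**3. Effect of a taper.** If the taper had halved the level, every entry halves. Scan 1 residuals become 6.2%, 20.1%, 27.9% and 37.1% of the treatment level, and the falls run from 5.5 to 17.3 points.

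For a linear dose taper over L days from steady state, the level at the last dose is (1 - 2^(-L/h)) / (L × ln 2 / h), and the scan 1 residual is that times 2^(-21/h):

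- h = 7, L = 14: 0.541 × 12.5% = 6.8%
- h = 7, L = 28: 0.338 × 12.5% = 4.2%
- h = 14, L = 14: 0.721 × 35.4% = 25.5%
- h = 14, L = 28: 0.541 × 35.4% = 19.1%

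So a taper of two to four weeks brings a 7-day drug inside a 10% tolerance but leaves a 14-day drug well outside it. A taper may do nothing for a depot already injected.

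**The case against.** The strongest reply is that no affected patient is shown. The documents name no prior drug, formulation or half-life, so the step from one fixed interval to biased scans needs slow drugs that may never appear in this sample. That stands. It limits the point to what the rule can assure; it does not show that the rule covers such drugs.

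The taper comes before the three weeks and lowers the starting level, and the stated purpose is freedom from significant influence, not complete elimination. This also stands. It is why no single half-life serves as the boundary and why the untapered residuals are upper figures for tapered oral drugs. But a taper of unstated length cannot assure clearance.

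A reader might infer that the first scan is contaminated, or that a few slow-drug patients will create a false trend. The documents support neither. They give no link from residual drug to [18F]DOPA uptake, in size or direction, and the public text states no sample size.

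A reader might also infer that Exclusion item 2 makes matters worse. It shows only that further drugs may be stopped. Nothing says that they are slow, and a plan to stop them leaves room for timing by drug.

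Finally, this is a feasibility study with no planned test that depends on full washout, and uncontrolled paired changes are open to time effects anyway. That lowers the stakes. Yet whether the washout rule works is itself feasibility information for the larger study. Stop dates may already be recorded, possibly under the linked screening protocols, in which case the remedy costs less still.

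**Conclusion.** The point holds as a gap in assurance. The same three weeks applies to every stopped drug, and for slow or depot drugs that does not secure the stated aim at scan 1. The working half-life limit is about 4 to 6 days with no taper effect and about 5 to 9 days if the taper had halved the level, taking a tolerated residual of 3% to 10%. Beyond it, the drug-level change between scans could be sizeable: 11 to 35 points of the last-dose level at the assumed half-lives, or about half that after a halving taper.

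This rests on first-order decline, assumed half-lives and a conventional clearance cut-off. How many patients are affected, and by how much the PET signal or mood score would move, cannot be found from the documents. It would go too far to say that the washout fails or that three weeks is wrong for ordinary drugs. This is a worthwhile, inexpensive improvement.

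**What to change.** Keep three weeks as the clinical minimum.

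- For each stopped drug, including any stopped under Exclusion item 2, use its name, formulation (oral or depot) and last-dose date to compute the half-lives elapsed at scan 1.
- Use the longer of the parent and active-metabolite half-lives, or the release half-life for a depot, from one source named in advance.
- Mark on the plots any patient with fewer than five half-lives elapsed for any stopped drug. Show the paired PET and mood changes with and without these patients.
- Keep the elapsed number itself, and repeat the display at the looser cut-off of 3.3 half-lives (10% left with no taper effect).

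**Cost.** One look-up per stopped drug, one extra set of plots, and last-dose date and formulation on the washout form if not already there. No visits or scans are added. A longer washout is not proposed: five half-lives would mean 5 × 7 = 35 to 5 × 49 = 245 days off drug for the assumed slow drugs, in depressed patients.

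**Downside.** The washed-out subset will be smaller in an already small study. The flag ignores the taper, so it may mark some patients who are in fact clear. It reveals possible residual drug but does not remove it, and it does nothing about natural course or regression to the mean.
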